### 11.2.1 Correlative Studies

Blood and Bone Marrow samples should be shipped the day of collection (Monday-Thursday) for next day delivery to the Masonic Cancer Center's Translational Therapy Lab (TTL). Refer to the Laboratory Manual for additional details. Pre-cycle 1 bone marrow sample is optional as it requires patient to undergo additional biopsy, while subsequent research bone marrow samples will be collected when the patient is having a bone marrow biopsy as part of clinical care.

TTL will process the samples to obtain mononuclear cells (MNC) and serum/plasma. TTL will analyze MNC by flow cytometry to evaluate NK cells for possible effects of therapy on phenotype and functional characteristics. Remaining MNC will be cryopreserved for batch analysis of effects on T cells and for other future testing.

Potential mechanisms of action for JAK/STAT inhibition in the prevention of GVHD and augmentation of GVL include alterations in cytokine signaling, alterations in T-cell trafficking through CXCR3 expression,

effects on cellular differentiation, and effects on antigen presenting cell function. An exploratory objective of this study will be to evaluate the effects of the combination on immune effectors and to measure changes in biomarkers of GVHD and GVL. To address this objective, correlative studies may include: cellular phenotyping; leukemia antigen expression; cytokine and other soluble biomarker expression; chemokine receptor expression and RNA transcript analysis. DNA samples may be used to test for genetic associations of response to therapy or GVHD. These studies will be performed at Washington University at the end of study using batch analysis of banked samples. Remaining cryopreserved samples may be used for future research studies at the discretion of the principle investigator.

### **11.3 Donor – Recommended Standard of Care**

Individual institutions may use local SOPs and clinical care guidelines, and unrelated donors will be screened through the NMDP.

## **12 Adverse Event Monitoring, Documentation, and Reporting**

Toxicity and adverse events will be classified and graded according to NCI's Common Terminology Criteria for Adverse Events V 5.0 (CTCAE) and reported on the schedule below. A copy of the CTCAE can be downloaded from the CTEP home page ([http://ctep.cancer.gov/protocolDevelopment/electronic\\_applications/ctc.htm#ctc\\_50](http://ctep.cancer.gov/protocolDevelopment/electronic_applications/ctc.htm#ctc_50)).

The following definitions of adverse events (AEs) and serious adverse events (SAEs) will determine whether the event requires expedited reporting via the OnCore SAE Report Form in addition to routine documentation in the OnCore AE case report form (CRF).

The reporting timeframes for SAEs, product related issues, and other reportable events are located in [Section 12.3](#).

Note: throughout this section the generic term "study drug" refers to the study related treatment (the ruxolitinib, decitabine, and DLI).

### **12.1 Adverse Event Terminology**

The following definitions are based on the Code of Federal Regulations Title 21 Part 312.32 (21CFR312.32(a)).

**Adverse Event:** Any untoward medical occurrence associated with the use of a drug in humans, whether or not considered drug related.

**Suspected Adverse Reaction:** Any adverse event for which there is a reasonable possibility that the drug caused the adverse event. For the purposes of IND safety reporting, "reasonable possibility" means there

is evidence to suggest a causal relationship between the drug and the adverse event. Suspected adverse reaction implies a lesser degree of certainty about causality than adverse reaction, which means any adverse event caused by a drug.

**Life-Threatening Adverse Event Or Life-Threatening Suspected Adverse Reaction:** An adverse event or suspected adverse reaction is considered “life-threatening” if, in the view of either the investigator or sponsor, its occurrence places the patient or subject at immediate risk of death. It does not include an adverse event or suspected adverse reaction that, had it occurred in a more severe form, might have caused death.

**Serious Adverse Event Or Serious Suspected Adverse Reaction:** An adverse event or suspected adverse reaction is considered “serious” if, in the view of either the investigator or sponsor, it results in any of the following outcomes:

- Death
- A life-threatening adverse event
- Inpatient hospitalization or prolongation of existing hospitalization
- A persistent or significant incapacity or substantial disruption of the ability to conduct normal life functions
- A congenital anomaly/birth defect
- An important medical event

Important medical events that may not result in death, be life-threatening, or require hospitalization may be considered serious when, based upon appropriate medical judgment, they may jeopardize the patient or subject and may require medical or surgical intervention to prevent one of the outcomes listed in this definition

**Unexpected adverse event or unexpected suspected adverse reaction:** An adverse event or suspected adverse reaction is considered “unexpected” if it is not listed in the investigator brochure or is not listed at the specificity or severity that has been observed; or, if an investigator brochure is not required or available, is not consistent with the risk information described in the general investigational plan or elsewhere in the current application, as amended.

**Expedited (Rapid) Reporting:** Certain events may require rapid notification to entities providing patient safety oversight (e.g. IRB) as detailed in [Section 12.3](#). For the IRB this is 5 business days from discovery.

The categories for AE attribution to study treatment are as follows:

- Definite – clearly related
- Probable – likely related
- Possible – may be related
- Unlikely – doubtfully related

- Unrelated – clearly not related

The following definitions are from the Masonic Cancer Center's Standard Operating Procedure (SOP) Deviation Reporting:

**Major Deviation:** A deviation or violation that impacts the risks and benefits of the research; may impact subject safety, affect the integrity of research data and/or affect a subject's willingness to participate in the research. Deviations that place a subject at risk, but do not result in harm are considered to be major deviations.

**Minor Deviation:** A deviation or violation that does not impact subject safety, compromise the integrity of research data and/or affect a subject's willingness to participate in the research.

## **12.2 AE Documentation**

AE reporting will occur via data entry into the study eCRF. AEs reported through expedited processes (e.g., reported to Incyte, IRB, FDA, etc.) must also be reported in routine study data submissions. Patients will be monitored for adverse events after the subject has signed the ICF through 30 days after the last dose of study drug. Adverse events recorded in the eCRFs include the following:

- CTCAE grade 3 and greater allergic reactions related to ruxolitinib or decitabine occurring until 30 days after the last treatment on study
- CTCAE grades 3 and greater organ toxicity (cardiac, dermatologic, gastrointestinal, hepatic, pulmonary, renal/genitourinary, or neurologic) occurring until 30 days after the last treatment on study
- aGVHD III-IV occurring until 3 months after the last cycle of treatment
- CTCAE grade 4 neutropenia lasting more than 14 days, occurring until 30 days after the last treatment on study
- CTCAE grades 3 and greater febrile neutropenia, or grade  $\geq 3$  neutropenia with documented infection, occurring until 30 days after the last treatment on study
- CTCAE grade 4 thrombocytopenia lasting more than 14 days if pre-treatment platelet count  $> 100 \times 10^9/L$ , occurring until 30 days after the last treatment on study

In addition any event meeting the definition of a serious adverse event (SAE) regardless of attribution that occurs during this period will be documented in the source document and recorded in OnCore.

After the final treatment visit, monitoring for adverse event will become less frequent based on the schedule in [Section 11](#) and only events at least possibly related to study treatment (based on the table above) will be documented upon knowledge.

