## 8.1 Chemotherapy Regimen

The administration of the preparative regimen will follow institutional drug and supportive care guidelines. Dose and/or schedule adjustments consistent with the standard of care may be made on an individual patient basis as needed for safety.

**Ruxolitinib** 5 mg twice daily orally beginning Day 1 and through Cycle 1. Consider dose increase to 10 mg twice daily in cycles 2 through 4 if platelets recover to over  $>100 \times 10^9/L$ . Ruxolitinib will continue through six months after the completion of the final cycle. See [section 8.4](#) for toxicity dose modification.

**Decitabine:** 20 mg/m^2 IV daily, on the following possible schedules: day 1-10 for cycles 1-2 (alternative: day 1-5 and day 8-12 with no weekend infusion); day 1-5 for cycles 3-4 (if CR achieved after Cycle 2). There are no dose modifications.

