## 11.1 Required Clinical Care Evaluations

	Screening within 28 days of study enrollment (within 14 days of C1D1 for eligibility labs)	Every Treatment Cycle		Between study cycles (day 29-56) 	Post DLI Visit (4-6 weeks after last DLI)	Follow-Up Q 3 months from the end of last cycle through 12 months
		During Decitabine admin	Day of DLI			
Written Consent	X					
Medical history	X					
Histological confirmation of diagnosis and staging	X					
Prior treatment	X					
Physical exam	X	X 	X		X	X
Provider assessment	X	X 	X			
Weight (Height also during screen)	X	X 				
Concomitant medications	X	X (day 1 each cycle)				
Karnofsky performance status	X			X		
ECG	X			X		
Type and Screen (ABO/RH/ Indirect Antiglobulin)	X					
Assessment of AEs	X	X	X		X	
Complete Blood Count with diff (CBC)	X	X 	X	X	X	X
Comprehensive Metabolic Profile (CMP) 	X	X 	X	X	X	X
HIV test	X					
Hepatitis B and C	X					
Pregnancy test (urine or serum) for WOCBP	X 			X		
Bone Marrow biopsy	X 			X 	X	
Relapse/progression status	X			X		
Survival status						X

MT2018-07: ruxolitinib, decitabine, and DLI for post-transplant relapse of AML or MDS

	Screening within 28 days of study enrollment (within 14 days of C1D1 for eligibility labs)	Every Treatment Cycle		Between study cycles (day 29-56) 	Post DLI Visit (4-6 weeks after last DLI)	Follow-Up Q 3 months from the end of last cycle through 12 months
		During Decitabine admin	Day of DLI			
Study treatment						
Decitabine		X (day 1-10 or day 1-5 & 8-12) 				
DLI			X (between 11-21 or 13-22) 			
Ruxolitinib		2 times a day				Through 6 months post end of last cycle
Research Nurse visit		Every two weeks			X	X

CMP to include sodium, potassium, chloride, creatinine, blood urea nitrogen, and liver function tests including AST, ALT, total bilirubin, and alkaline phosphatase

For women of childbearing potential (WOCBP): urine or serum pregnancy test within 14 days prior to study registration. If a urine test is positive or cannot be confirmed as negative, a serum pregnancy test will be required.

Continuous reassessment for eligibility to proceed to subsequent cycles

Results taken out of window may be used as enrollment verification and will not be considered a deviation.

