## 12.3 SAE Documentation and MCC Reporting Requirements

Individual institution reporting requirements are listed in [section 12.5](#).

All SAEs are documented using the MCC OnCore SAE Report Form and reported within the timeframes indicated below:

Agency	Criteria for reporting	Timeframe	Form to Use	Submission address/ fax numbers
U of MN IRB	Events requiring prompt reporting including, but not limited to unanticipated death of a locally enrolled subject(s); new or increased risk; any adverse event that require a change to the protocol or consent form or any protocol deviation that resulting in harm. For a complete list refer to http://www.research.umn.edu/irb/guidance/ae.htm l#.VC7xral0-sh	Within 5 business days of event discovery	MCC SAE Report Form	ETHOS copy SAEs to Incyte at [contact] (note: Incyte does not need copies of deviations)
	Deviations from the protocol, per current IRB reporting requirements		Deviation Report	
FDA	Unexpected and fatal or unexpected and life threatening suspected adverse reaction	no later than 7 Calendar Days	MCC SAE Report Form	Submit to FDA as an amendment to IND
	1) Serious and unexpected suspected adverse reaction or 2) increased occurrence of serious suspected adverse reactions over that listed in the protocol or investigator brochure or 3) findings from other sources (other studies, animal or in vitro testing)	no later than 15 Calendar Days		
	Events that trigger an early study stopping rule.	no later than 7 Calendar Days	Event Form	
Incyte Corporation	Every SAE, regardless of suspected causality (eg, relationship to study drug(s) or study procedure or disease progression), occurring after the subject has signed the ICF through the last study visit (or 30 days) after the last dose of study drug, whichever is later) must be reported to the Incyte within 24 hours of learning of its occurrence, Incyte may request follow-up and other additional information from the Sponsor Investigator.	Within 24 hours of event discovery	MCC SAE Report Form	[contact]
Masonic Cancer Center SAE Coordinator	Events that count toward early study stopping rule.	At time of reporting	Event Form	SAE Coordinator [contact] with copy to Incyte

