### **14.3 Correlative Endpoints**

- Incidence and severity of adverse events (AEs) and serious AEs (SAEs) until 3 months after day 1 of the last received cycle
- Correlative studies: T cell and NK cell subset analysis by flow cytometry, correlation between TP53 mutation and response, clonal dynamics during and after the course of therapy

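### AE collection in 12.2 can end before the AE endpoint window in 14.3 does, so non-serious events are under-counted in patients who stop all study drug early

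*Combined protocol and SAP*

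**What the plan says.** The endpoint in 14.3, repeated in the synopsis and in 1.3, is "Incidence and severity of adverse events (AEs) and serious AEs (SAEs) until 3 months after day 1 of the last received cycle".

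Collection is governed by 12.2: "Patients will be monitored for adverse events after the subject has signed the ICF through 30 days after the last dose of study drug". Section 12.2 then lists the events that go into the eCRF. Each is limited to those "occurring until 30 days after the last treatment on study", except grade III–IV acute GVHD, which is recorded to 3 months after the last cycle. After the final treatment visit, "only events at least possibly related to study treatment" are documented, and then only as they become known. SAEs of any attribution are recorded, but only within the same monitoring period.

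The introduction to section 12 counts ruxolitinib, decitabine and DLI all as study drug. Section 8.1 states: "Ruxolitinib will continue through six months after the completion of the final cycle". Section 8.8 lets ruxolitinib continue after DLI has stopped, but not once unacceptable toxicity has developed.

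Sections 12.3 and 12.5 set a different SAE period. "Every SAE, regardless of suspected causality" is to be reported through the last study visit or 30 days after the last dose, whichever is later.

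In the calendar in 11.1, the row "Assessment of AEs" is marked at screening, during decitabine, on the day of DLI and at the post-DLI visit 4–6 weeks after the last DLI. It has no mark in the 3-monthly follow-up column. Section 15.2 summarises AEs as frequencies and proportions of patients.

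**The concern.** The endpoint window is fixed relative to day 1 of the last cycle, while the collection window moves with the last dose. A patient who stays on ruxolitinib is collected well past the endpoint date. A patient who stops everything early is not. The two groups differ systematically, because 8.8 lists unacceptable toxicity and disease progression among the reasons for stopping. Time under observation therefore depends on tolerability and disease course, and a simple proportion makes no allowance for that.

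The protocol's own risk section shows what could be missed. Section 9.3 says marrow aplasia and pancytopenia may appear between 1 and 6 months after a DLI. Prolonged grade 4 neutropenia and thrombocytopenia are listed eCRF events. If a DLI was the last study drug, systematic collection ends about when that risk period opens. A later cytopenia is then recorded only if it is judged at least possibly related and someone learns of it, or if it qualifies as an SAE. In relapsed AML or MDS that attribution is hard to make. This is the trial's only general AE endpoint.

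**Working it through.** The plan gives no figure to reproduce; the check counts days between its own windows.

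**Convention.** Take 3 months as 90 days, so the endpoint window is days 1 to 91 of the last cycle. With 3 months as 92 days, each gap below is 2 days longer.

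**Formulas.** For a last dose of any study drug on day d, systematic collection ends on day d + 30, and gap = 91 − (d + 30) = 61 − d. There is no gap when d is 61 or later (63 or later with 92 days).

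| Last study drug | Collection ends | Gap | Share of 91 days |
|---|---|---|---|
| Day 10 (last decitabine, 10-day schedule) | day 40 | 51 | 56% |
| DLI day 11 | day 41 | 50 | 55% |
| DLI day 21 | day 51 | 40 | 44% |
| Day 28 | day 58 | 33 | 36% |
| Day 56 | day 86 | 5 | 5% |

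On the 5-day schedule (8, Table 3) a final DLI on day 6–16 gives 61 − 6 = 55 to 61 − 16 = 45 days.

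**Planned ruxolitinib.** Take 6 months as 180 days after a 28- to 56-day cycle. Collection then runs to 28 + 180 + 30 = day 238, or to 56 + 180 + 30 = day 266. That is 147 to 175 days beyond the endpoint, so the 12.2 window leaves no gap.

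**Scheduled AE assessment (11.1).** The post-DLI visit falls 28–42 days after the last DLI:

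- 10-day schedule: 11 + 28 = day 39 to 21 + 42 = day 63
- 5-2-5 schedule: 13 + 28 = day 41 to 22 + 42 = day 64
- 5-day schedule: 6 + 28 = day 34 to 16 + 42 = day 58

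When the DLI is given in the last cycle, this last scheduled assessment lies on about day 34–64. The final 91 − 64 = 27 to 91 − 34 = 57 endpoint days have none, whether or not ruxolitinib continues. Section 12.2 refers to the section 11 schedule for later monitoring, but that schedule has no AE mark there.

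**What is collected during the gap.**

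- Grade III–IV acute GVHD: recorded to 28 + 90 = day 118 or 56 + 90 = day 146, past day 91.
- SAEs: required by 12.3 and 12.5 to the last study visit if that is later. Section 12.2 also says that events reported through expedited routes must enter the routine study data.
- Other listed events, at least possibly related: passive documentation only.
- Other listed events, unrelated and non-serious: not recorded.

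**Effect on the estimate.** Missed events can only lower a proportion. The shortfall is the share of patients whose first event of a given type falls in the gap and goes unrecorded. The documents give neither the number of early stoppers nor an event rate for the gap, so the shortfall cannot be calculated.

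**The case against.** Several stronger readings are tempting, and the documents do not support them.

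A reader might infer that all AE capture stops at 30 days. It does not: grade III–IV acute GVHD, SAEs and possibly related events each have a longer route. The stopping rule in 15.4 uses the longer GVHD window and is unaffected.

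A reader might infer that SAE incidence is biased in the same way. Sections 12.3 and 12.5 require SAEs of any causality through the last study visit, and 12.2 sends expedited reports into the study data. What remains is a conflict of wording, because 12.2 limits SAE recording to its own shorter period.

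A reader might take the 51-day gap as typical. It needs a last dose on day 10, with no DLI and no ruxolitinib afterwards. Ruxolitinib is planned for six more months, and stopping DLI or decitabine alone opens no gap in 12.2 if ruxolitinib continues past about day 61.

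A reader might infer that a patient with no DLI in the last cycle has no assessment tied to it. AE assessment is marked during decitabine in every cycle, and follow-up is timed from the end of the last cycle.

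It is also fair that the endpoint is correlative and descriptive, and that follow-up visits include physical examination, blood counts, chemistry and a research nurse contact, at which events may surface. Under 8.9, patients who start new anti-cancer treatment or enter hospice are followed for survival only. Collecting everything to 3 months would conflict with that rule and could attribute the next therapy's toxicity to this regimen.

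These points narrow the problem without removing it. Passive recording of related events does not replace systematic collection, and nothing in 12.2 brings its window into line with 14.3.

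**Conclusion.** The concern holds for listed non-serious events other than grade III–IV acute GVHD. If ruxolitinib, decitabine and DLI all stop before about day 61 of the last cycle, roughly 5 to 51 of 91 endpoint days lack systematic capture for last doses between day 56 and day 10. The figure is 40 to 50 days when the last study drug is a day 11–21 DLI, and somewhat more on the 5-day schedule. Separately, no patient has an AE assessment scheduled in 11.1 after the post-DLI visit.

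The bias in non-serious AE incidence is downward and of unknown size. The direction rests on early stopping being related to toxicity and progression, as 8.8 implies, and on analysis by unadjusted proportions. The day counts rest on 3 months being 90–92 days. The reading of 11.1 rests on a table extracted from PDF. SAEs are largely covered, apart from the wording conflict and a possibly early last study visit for patients in survival-only follow-up. The primary survival analysis is untouched. The mismatch should be corrected, but it does not threaten the trial's main conclusion.

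**What to change.** - **12.2, AEs:** collect the listed AEs, regardless of attribution, to the later of 30 days after the last dose and 3 months after day 1 of the last received cycle. Keep the existing longer window for grade III–IV acute GVHD.
- **12.2 with 8.9:** for patients who move to survival-only follow-up, end the added collection at that point and report them as having shorter observation.
- **11.1:** mark AE assessment at the first 3-monthly follow-up visit (about day 118–146 of the last cycle), covering back to the previous assessment.
- **12.2, SAEs:** align the recording period with 12.3 and 12.5.

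This closes the gap for every patient who remains in full follow-up. For a last study drug of a day 11–21 DLI it adds 40 to 50 days of collection; for a patient who completes planned ruxolitinib it adds none to the 12.2 window. The cost is amendment wording and a few more weeks of AE entry for early stoppers, at a visit that already exists. Recall over the interval between assessments will be imperfect, and patients in survival-only follow-up will still have shorter observation.

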## 8.2 DLI

Within 10 days after the last dose of decitabine in each cycle, a DLI product from the previous donor (either remaining from the original transplant unit, or a new unit) will be infused. Donor lymphocytes will be obtained by lymphapheresis from the same allogeneic donor used for transplantation. For local related donors, lymphocyte collections will be performed using standard automated mononuclear cell collection techniques by the University of Minnesota Blood Bank or study affiliate site's institutional guidelines. For unrelated donors or non-local related donors, the lymphocyte collection will be performed at an outside facility according to procedures set by the National Marrow Donor Program. If the collection is non-local, coordination for the timing of the cell collection and the ability to transport the cells to the study site is required. Similarly, for local related donors, the timing of collection (same day as infusion vs. cryopreserved) is according to the collaborating centers' institutional guidelines.

The duration of DLI will be determined according to the collaborating centers' institutional guidelines. DLI will be administered according to a donor-dependent dose-escalation algorithm ([Table 4](#)). In the absence of new GVHD (any grade), the dose of DLI for the next cycle will be higher than the previous cycle. Otherwise, the dose will remain the same. DLI will be given without adding immunosuppressive medications and without conditioning. Addition of immunosuppressive medications as indicated to treat grade I acute GVHD or other non-GVHD steroid-responsive conditions is allowed.

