#### Acute Graft-Versus-Host Disease

Infusion of donor lymphocytes into patients who relapse post allogeneic bone marrow transplantation has frequently resulted in development of acute graft-versus-host disease with involvement of the skin and liver, often requiring treatment. Despite treatment, some cases of GVHD have been of high grade and deaths from GVHD have been reported. GVHD may occur between 1 and 24 weeks post-infusion of the donor lymphocytes. Patients will have regular assessment for development of new or worsening of existing GVHD during the entire study period.

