**12.4 Early Stopping Rule Events Documentation and Reporting Requirements**

The following events count toward an early study stopping rule per [Section 15.4](#) and must be reported to the MCC Affiliate Sites Manager and to Incyte Pharmaceuticals using the Event Form found OnCore under the reports tab: grade III-IV aGVHD until 3 months after the last cycle of treatment.

An event that counts toward an early stopping rule does not necessarily constitute a SAE and should be reported as such only if they meet the criteria for reporting as defined in [Section 12.3](#).

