### **14.2 Secondary Endpoints**

Secondary endpoints of safety and efficacy are measured as below.

- OS at 12 months
- Cumulative incidence of grade II-IV acute graft-versus-host disease (aGVHD II-IV) at 3 months
- PFS at 6 and 12 months in patients
- Cumulative incidence of relapse at 6 and 12 months
- Complete remission (CR) at 6 and 12 months
- Cumulative incidence of non-relapse mortality (NRM) at 6 and 12 months
- Best response until next line of treatment, death, or last follow up, whichever occurs sooner

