### **Secondary and exploratory analysis**

Analysis of secondary endpoints will be primarily descriptive. Progression-free survival will be estimated by Kaplan-Meier curves. Cumulative Incidence will be used to estimate the probability of relapse and acute GVHD, treating non-event death as a competing risk. Likewise, relapse will be treated as a competing risk when estimating the probability of non-relapse mortality. Response and the number of patient in complete remission will be estimated with simple proportions. Summary statistics using frequencies and proportions of patients will be used to assess adverse and severe adverse events and medians, ranges and descriptive plots for immune therapy. The correlation between *TP53* mutation and response will be assessed with a chi-square test or Fisher's exact test depending on expected cell frequencies. Similar statistics will be used for the correlation against clonal dynamics curing and after the course of therapy.

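### The endpoint is grade II-IV acute GVHD, but the plan names no form or visit that records a non-serious grade II case, so the II-IV incidence may be understated

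*Combined protocol and SAP*

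**What the plan says.** - **Endpoint (14.2):** "Cumulative incidence of grade II-IV acute graft-versus-host disease (aGVHD II-IV) at 3 months". No time origin is given.
- **Analysis (15.2):** "Cumulative Incidence will be used to estimate the probability of relapse and acute GVHD, treating non-event death as a competing risk".
- **Recording (12.2):** "Adverse events recorded in the eCRFs include the following". The list sets a severity threshold item by item, and its one GVHD item is "aGVHD III-IV occurring until 3 months after the last cycle of treatment". Any SAE is recorded as well. After the final treatment visit, monitoring follows the section 11 schedule, and only events at least possibly related to treatment are documented, with a pointer back that appears to mean this same list.
- **Stopping rule (12.4):** the event is "grade III-IV aGVHD until 3 months after the last cycle of treatment".
- **Calendar (11.1):** there is no GVHD row. The row "Assessment of AEs" is marked at screening, during decitabine, on the day of DLI and at the post-DLI visit. It is blank between cycles and in follow-up. Physical exam is blank between cycles only.
- **Promise (9.3):** "Patients will have regular assessment for development of new or worsening of existing GVHD during the entire study period".
- **Rules that presuppose a GVHD assessment:** section 8.2 states "In the absence of new GVHD (any grade), the dose of DLI for the next cycle will be higher than the previous cycle", and criterion 8.5.6 bars a further cycle after new GVHD other than grade I acute.
- **Appendix II:** grading tables for acute GVHD grades I to IV, but fields for recording a case (such as diagnosis date and organs) only for late acute and chronic GVHD.

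**The concern.** A cumulative incidence of grade II-IV acute GVHD with death as a competing risk needs, for each patient, whether grade II was reached and on what date. The recording threshold in 12.2 sits one grade above the endpoint's and coincides with the stopping-rule event instead. A site that follows 12.2 to the letter has no instruction to enter a non-serious grade II case, and the calendar gives no visit at which GVHD is to be staged. Data that were never collected cannot be recovered at analysis. The error can only go one way: acute GVHD, the main toxicity of DLI according to section 2.1, would look less frequent than it was.

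**Working it through.** **1. The plan's own acute GVHD figure.** The only computed figure is the grade III-IV stopping rule in 15.4: boundary 2/2, 3/6, 4/10, 5/15, 6/21, 7/27, 8/33; at most 5% stopping at a true rate of 10%; 86% at 30%; 34 patients. Stepping through the patients one at a time, the probability of early stopping is the sum over n of P(event count first reaches the boundary at patient n), with binomial increments. This gives 4.87% at 10% and 86.1% at 30%. Both stated figures reproduce. They concern grade III-IV only. The documents give no rate for grade II or grade II-IV.

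**2. Routes by which a grade II case could reach the database.**

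| Place | What it provides | Grade and onset date of a non-serious grade II case? |
|---|---|---|
| 12.2 list | Acute GVHD III-IV | No |
| 12.2 SAE clause | Any serious event | Serious cases only |
| 12.2 organ-toxicity item | CTCAE grade 3 or greater, by organ | Some cases, without a GVHD grade |
| 8.2 and 8.5.6 | GVHD must be recognised before the next cycle or DLI | No dated record is called for; nothing after the last cycle |
| 11.2 | Blood sample at GVHD diagnosis, any grade | A date, no grade |
| 11.1 | Exam and AE assessment at several visits | No GVHD item |
| Appendix II | Acute grading scale | Scale only |
| 13.2 | Protocol-specific eCRFs | Possibly; the forms are not in the documents |

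No row clearly supplies both items.

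**3. The interval after the last DLI.** On the 10-day schedule, DLI falls on day 11-21 and the post-DLI visit 28-42 days later:
- Post-DLI visit: 11 + 28 = day 39 to 21 + 42 = day 63 of the last cycle.
- First follow-up visit, taking 3 months as 91 days after a 28-day last cycle: 28 + 91 = day 119.
- Interval between them: 119 - 63 = 56 to 119 - 39 = 80 days. The day-119 visit has an exam but no AE mark.
- If the last cycle could run 56 days: 56 + 91 = day 147, and 147 - 63 = 84 to 147 - 39 = 108 days. This depends on reading days 29-56 as part of a last cycle, although Table 1 labels them as between cycles.

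Section 9.3 puts GVHD onset at 1 to 24 weeks after DLI, so cases can arise in this interval.

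How much of the interval bears on the endpoint depends on the missing time origin. If the 3 months run from the last cycle, as in 12.2 and 12.4, all or most of it does. If they run from cycle 1 day 1, as overall survival does in 15.1, the window closes at day 91. A patient with one cycle then has 91 - 63 = 28 to 91 - 39 = 52 days after the post-DLI visit. A patient with three cycles on the 10-day schedule reaches that visit no earlier than 56 + 39 = day 95, after the window has closed.

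**4. Size, as an illustration.** Recorded rate = rate(III-IV) + rate(II) × (1 - m), where m is the share of grade II cases not captured. Rate(III-IV) = 10% is the plan's figure in 15.4. The true II-IV rate of 20-40% is my assumption, so rate(II) = 10-30%.

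| m | Recorded II-IV rate | Missing of 32 |
|---|---|---|
| 0 | 20-40% | 0 |
| 0.5 | 15-25% | 1.6-4.8 |
| 1 | 10% | 3.2-9.6 |

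**The case against.** The strongest reply is that 12.2 is a safety list, not the data specification for endpoints. It is introduced as what the eCRFs include, so it is not stated to be exhaustive. The eCRFs are protocol specific, are approved by the principal investigator and the biostatistician, and are not shown; they may well contain an acute GVHD form. Other sections require GVHD to be recognised: regular assessment in 9.3, separation of grade I from higher grades at each re-screening, the any-grade condition before the next DLI, and the blood sample at diagnosis. The calendar also has research nurse visits every two weeks during treatment and again at the post-DLI and follow-up visits.

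Most of this stands, and it limits the point to a risk. Three things remain. Recognising GVHD for a treatment decision is not the same as recording a graded, dated event. Re-screening ends with the last cycle. And the comparison with other endpoints absent from 12.2 does not carry over: relapse and survival have their own rows in 11.1, and GVHD has none.

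A reader might infer more in three ways, none of which the documents support:
- *Grade II cases will be lost and the II-IV rate will collapse to about 10%.* This assumes zero capture, which the SAE route alone contradicts, and it treats unseen forms as if they were known to lack the item.
- *The stopping rule is compromised.* Grade III-IV is the one GVHD item listed, and sections 12.4 and 12.5 give it its own event form and 24-hour reporting.
- *DLI is escalated without an examination.* The 11.1 calendar and its footnote 8 place an exam on day 1 of each cycle, and another is marked on the day of DLI.

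**Conclusion.** The mismatch is real and should be reconciled. The endpoint needs grade II cases with dates, the eCRF list starts at grade III, and no section or visit is assigned to record the rest. The II-IV incidence may be understated, most plausibly after the last DLI. The amount cannot be computed from the documents. It lies between zero, if an unseen form captures every case, and the whole grade II share; under the assumed 20-40% true rate, that upper end is about 3 to 10 of 32 patients. The 56-80 day interval after the post-DLI visit assumes a 28-day last cycle and the 10-day schedule, and its relevance depends on the undefined 3-month origin. The endpoint is secondary and descriptive, so the sample size, the primary analysis and the stopping boundary are unchanged.

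**What to change.** - **12.2:** replace the GVHD item with acute GVHD of any grade, recording onset date (including the date grade II was first reached), organ stages and maximum grade per Appendix II, to the end of the endpoint window. Keep grade III-IV as the stopping-rule subset.
- **11.1:** add a GVHD staging row at visits that already carry an exam: day 1 of each cycle, day of DLI, post-DLI visit, and follow-up visits through the window. Mark AE assessment at the first follow-up visit.
- **14.2:** state the time origin of the 3-month incidence, so that the collection window and the endpoint match.
- If an acute GVHD eCRF already exists, name it in 12.2 and confirm that it holds these fields.

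The cost is an amendment to wording and calendar and slightly more data entry. Staging uses exams and laboratory tests already scheduled, so no new procedure is needed. No dose, treatment rule, sample size or boundary changes.
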